I agree to ensure that the confidential information contained in this document will not be used for any purpose other than the evaluation or conduct of the clinical investigation without the prior written consent of Amgen Inc.

Signature

Name of Investigator

Date (DD Month YYYY)

Protocol Synopsis

Title: A Multicenter, Randomized, Double-blind, Placebo-controlled, Study to Compare the Efficacy and Safety of Romosozumab with Placebo in Postmenopausal South Korean women with Osteoporosis

Study Phase: 3

Indication: Osteoporosis in postmenopausal women

Primary Objective: To evaluate the effect of treatment with romosozumab for 6 months compared with placebo on percent changes in bone mineral density (BMD) at the lumbar spine as assessed by dual-energy x-ray absorptiometry (DXA) in postmenopausal women with osteoporosis.

Secondary Objective: To evaluate the effect of treatment with romosozumab for 6 months compared with placebo on the percent changes in DXA BMD at the total hip and femoral neck.

Exploratory Objective: To evaluate the effect of treatment with romosozumab for 6 months compared with placebo on percent changes in bone turnover markers (BTM): bone formation marker procollagen type 1 N-telopeptide (P1NP) and bone resorption marker serum type I collagen C-telopeptide (CTX).

Safety Objective: To characterize the safety and tolerability of treatment with romosozumab for 6 months compared with placebo as determined by a review of reported adverse events, laboratory data, vital signs, and the formation of anti-romosozumab antibodies over the 6-month treatment period, and adverse events and the formation of anti-romosozumab antibodies for the overall study period (6-month treatment period followed by the 3-month follow-up period).

Pharmacokinetics (PK): To characterize the serum romosozumab concentration

Hypotheses: The primary clinical hypothesis is that in South Korean postmenopausal women with osteoporosis, the mean percent change in lumbar spine BMD in subjects receiving romosozumab will be superior to that of those receiving placebo at month 6. It is hypothesized that changes in BMD at the lumbar spine in subjects receiving romosozumab will be at least 6.6% greater than in subjects receiving placebo. The safety hypothesis is that romosozumab treatment for 6 months is well tolerated in South Korean women with osteoporosis.

Primary Endpoint: Percent change from baseline in DXA BMD at the lumbar spine at month 6

Secondary Endpoint: Percent change from baseline in DXA BMD at the femoral neck and total hip at month 6.

Exploratory Endpoints: Percent changes from baseline in bone turnover markers (BTM): bone formation marker procollagen type 1 N-telopeptide (P1NP) and bone resorption marker serum type I collagen C-telopeptide (CTX) at months 1, 3, and 6

Safety Endpoints:

For the 6-month treatment period:

- Subject incidence of adverse events by system organ class and preferred term
- Changes from baseline in laboratory assessments (serum chemistry and hematology) and shifts from baseline to the worst value between baseline and month 6
- Changes from baseline in vital signs
- Incidence of subjects with anti-romosozumab antibodies at months 1, 3, and 6

For the overall study period (6-month treatment period followed by the 3-month follow-up period):

- Subject incidence of adverse events by system organ class and preferred term
- Subject incidence of the formation of anti-romosozumab antibodies

Pharmacokinetic Endpoint: Romosozumab serum concentration at months 1, 3, and 6

Study Design: This is a multicenter, randomized, double-blind, placebo-controlled study in approximately 60 South Korean postmenopausal women with osteoporosis. The study is designed to evaluate if treatment with romosozumab once a month (QM) for 6 months compared with placebo is effective in increasing BMD at the lumbar spine. In addition, the study will assess the effect of treatment with romosozumab QM for 6 months compared with placebo on BMD at the femoral neck and total hip.

Approximately 60 subjects will be randomized in a 1:1 ratio to receive 210 mg romosozumab subcutaneous (SC) QM (approximately 30 subjects) or matched placebo SC QM (approximately 30 subjects), respectively, in a blinded fashion for the duration of the 6-month treatment period.

Upon completion of the 6-month treatment period, subjects will be followed for an additional 3 months to ensure appropriate follow-up for anti-romosozumab antibody formation.

From screening to end of study (EOS), subjects will receive daily calcium and vitamin D supplementation. In addition, subjects with a serum 25 (OH) vitamin D level of ≥ 20 ng/mL and ≤ 40 ng/mL at screening will receive an initial loading dose of vitamin D after randomization.

Approximately 10 sites in South Korea will participate in this study. Sites that do not enroll subjects within 2 months of site initiation may be closed.

Sample Size: Approximately 60 subjects will be enrolled in the study.

Summary of Subject Eligibility Criteria: The study will enroll ambulatory postmenopausal Korean women, ≥ 55 to ≤ 90 years of age at randomization with a DXA BMD T-score ≤ -2.50 at the lumbar spine, total hip or femoral neck. Subjects must have at least 2 vertebrae in the L1 through L4 region and at least 1 proximal femur evaluable by DXA. Subjects with a BMD T-score ≤ -4.0 at the lumbar spine, total hip or femoral neck and subjects with a history of hip fracture are ineligible for the study. For a full list of eligibility criteria, please refer to [Section 4.1](#).

Investigational Product: Romosozumab or matching placebo administered by prefilled syringe (PFS).

Amgen Investigational Product Dosage and Administration: Romosozumab 210 mg or matching placebo will be administered QM for 6 months as an SC injection via PFS at day 1, month 1, month 2, month 3, month 4, and month 5. All dosing will be administered in-clinic.

Non-Amgen Non-investigational Product Dosage and Administration: From screening to EOS, subjects will receive daily calcium and vitamin D supplementation that at a minimum is in the range of 500 to 1000 mg elemental calcium and 600 to 800 IU vitamin D. In addition, subjects with a serum 25 (OH) vitamin D level of ≥ 20 ng/mL and ≤ 40 ng/mL at screening will receive an initial loading dose of 50 000 to 60 000 IU vitamin D after randomization, preferably by the oral route. Subjects with a serum 25 (OH) vitamin D level of > 40 ng/mL at screening may also receive the vitamin D loading dose at the principal investigator's discretion.

Procedures: Informed consent; demographics; medical, medication, fracture, tobacco, alcohol, and substance use history; physical examination; physical measurements (height and weight); vital signs (blood pressure, heart rate, respiratory rate, and temperature); concomitant medications; serious adverse event reporting; adverse event reporting; laboratory assessments (serum chemistry, hematology, serum protein electrophoresis, hepatitis B and C testing, serum 25 (OH) vitamin D, intact parathyroid hormone (iPTH), pharmacokinetics, anti-romosozumab antibody, BTMs; DXA scan of the lumbar spine and proximal femur; IP administration; daily calcium and vitamin D supplementation; and if applicable, vitamin D loading dose administration.

For a full list of study procedures, including the timing of each procedure, please refer to [Section 7](#) and the Schedule of Assessments ([Table 1](#)).

Statistical Considerations:

Primary Efficacy Endpoint:

The analysis to assess the percent change from baseline in lumbar spine DXA BMD at month 6 will employ an analysis of covariance (ANCOVA) model. The ANCOVA model will include treatment group, baseline value of BMD, machine type and interaction of baseline BMD value and machine type as independent variables. Summaries for the results will include least-squares

means point estimates of the percent change from baseline for each treatment arm. The variance structure will allow for heterogeneity between treatments. The 2-sided 95% confidence interval (CI) and associated p-value will be provided for the difference between the least-squares means for romosozumab and placebo.

Conclusions for the primary efficacy hypothesis of different efficacy of romosozumab compared with placebo at lumbar spine BMD will be made using a 2-sided test with type 1 error rate of 0.05.

Secondary Efficacy Endpoints:

For the secondary efficacy BMD endpoints (total hip and femoral neck at month 6), the percent change from baseline in DXA BMD will employ an ANCOVA model. The ANCOVA model will include treatment group, baseline value of BMD, machine type and interaction of baseline BMD value and machine type as independent variables. Summaries for the results will include least-squares means point estimates of the percent change from baseline for each treatment arm. The variance structure will allow for heterogeneity between treatments. The 2-sided 95% CI and associated p-value will be provided for the difference between the least-squares means for romosozumab and placebo.

Exploratory Efficacy Endpoints:

For P1NP and CTX, descriptive statistics will be presented by treatment group at each visit for both actual values and the percent change from baseline values. Graphs depicting median and interquartile ranges by treatment group for percent change over time will be provided.

Safety Endpoints:

Safety analyses will include assessments of treatment-emergent adverse events, IP exposure, clinical laboratory assessments, vital signs, and anti-romosozumab antibodies. The safety analysis set will be used for these analyses. There is no planned inferential statistical testing in the safety analyses. All categorical endpoints will be summarized using the number and percent of subjects. All continuous endpoints will be summarized using descriptive statistics including mean, standard deviation, minimum, quartiles, maximum, and number of subjects.

Pharmacokinetic Endpoint:

Trough serum concentration values determined from subjects may be summarized in tabular form and presented graphically. Additional pharmacokinetic analyses will be performed as appropriate.

[figure not shown]
For a full description of statistical analysis methods, please refer to [Section 10](#).

Sponsor: Amgen, Inc.

Data Element Standards
Version(s)/Date(s):

Version 5/20 March 2015

Study Design and Treatment Schema

Abbreviations: D=day; IP=investigational product; M=month; n=number; QM=once monthly; SC=subcutaneous;

Study Glossary

Abbreviation or Term	Definition/Explanation
ALP	alkaline phosphatase
ALT	alanine transferase
ANCOVA	analysis of covariance
AST	aspartate aminotransferase
BMD	bone mineral density
BMI	body mass index
BP	blood pressure
BTM	bone turnover markers
CI	confidence interval
CRF	case report form
CTCAE	Common Terminology Criteria for Adverse Events
CTX	collagen C-telopeptide
DILI	drug-induced liver injury
DXA	dual-energy x-ray absorptiometry
EDC	electronic data capture
End of Study (end of trial)	defined as when the last subject is assessed or receives an intervention for evaluation in the study
End of Study (primary completion)	defined as when the last subject is assessed or receives an intervention for the purposes of final collection of data for the primary endpoint
End of Study for Individual Subject	defined as the last day that protocol-specified procedures are conducted for an individual subject
End of Treatment	defined as the last assessment for the protocol-specified treatment phase of the study for an individual subject
EOI	Event of Interest
EOS	end of study
ET	early termination
GCP	Good Clinical Practice
HepBcAb	total hepatitis B core antibody
HepBsAg	Hepatitis B Surface Antigen
ICF	informed consent form
ICH	International Conference on Harmonisation
INR	international normalized ratio

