1.3 Exploratory

To evaluate the effect of treatment with romosozumab for 6 months compared with placebo on percent changes in bone turnover markers (BTM): bone formation marker procollagen type 1 N-telopeptide (P1NP) and bone resorption marker serum type I collagen C-telopeptide (CTX).

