2.2 Amgen Investigational Product Background

Sclerostin, the protein product of *SOST*, produced by the osteocyte, is an inhibitor of osteoblast-mediated bone formation ([Poole et al, 2005](#); [Van Bezooijen et al, 2004](#); [Winkler et al, 2003](#); [Balemans et al, 2001](#); [Brunkow et al, 2001](#)). Humans with inherited sclerostin deficiencies have high bone mass and BMD throughout the skeleton and are resistant to fractures ([Hamersma et al, 2003](#); [Vanhoenacker et al, 2003](#)).

Administration of a sclerostin antibody, resulting in the blocking of the inhibitory effect of sclerostin on bone formation, has been shown to increase bone formation, BMD, and bone strength in multiple animal models (non-osteopenic and osteopenic rats and monkeys) ([Ominsky et al, 2015](#); [Li et al, 2014](#); [Li et al, 2010](#); [Ominsky et al, 2010](#)).

Romosozumab is a humanized monoclonal antibody that is designed to bind and inhibit sclerostin, thereby promoting osteoblast differentiation and activity, leading to an increase in bone formation, BMD, and bone strength. Proof of biological activity for romosozumab has been established in a first-in-human, ascending-single-dose study in healthy men and postmenopausal women, an ascending-multiple-dose study in healthy

men and postmenopausal women with low bone mass and a phase 2 dose-ranging study in postmenopausal women with low bone mass. In all studies, treatment with romosozumab was generally well tolerated and resulted in a transient increase of the bone formation marker P1NP and a decrease in the bone resorption marker serum CTX. Increases in BMD at the lumbar spine, total hip and femoral neck have also been demonstrated, by DXA, and quantitative computed tomography.

The ability of romosozumab to prevent fractures in postmenopausal women with osteoporosis is currently being evaluated in the following phase 3 studies:

- Placebo-controlled study designed to evaluate if treatment with romosozumab for 12 months is effective in reducing the risk of new vertebral and nonvertebral fractures
- Alendronate-controlled study designed to evaluate if treatment with romosozumab for 12 months followed by alendronate treatment, is effective in reducing the incidence of clinical fractures and new vertebral fractures

Refer to the specific sections of the Romosozumab Investigator's Brochure for additional information related to the physical, chemical, and pharmaceutical properties and formulation.

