6.6 Arithmetic Calculations

Age at Randomization Date

Number of whole years from a subject’s birthdate to the randomization date as recorded on the eCRF.

Estimated Glomerular Filtration Rate (eGFR)

$eGFR(mL/min/1.73 m^2)=175 \times (S_{cr, std})^{-1.154} \times (Age)^{-0.203} \times (0.742 \text{ if female}) \times (1.212 \text{ if African American})$

where $S_{cr, std}$ is serum creatinine in standard unit (mg/mL)

Percent Change From Baseline

The change from baseline value divided by baseline value and multiplied by 100:

$((\text{value at date of interest} - \text{baseline value}) / \text{baseline value}) * 100.$

Subject Incidence for AEs

The subject incidence for a given event in a given time period is defined as the number of subjects with ≥ 1 reported occurrence of the event divided by the number of subjects who are at risk for having the event at the beginning of the given time period. For subjects with multiple occurrences of the same event, the event will only be counted once per subject.

BMD Value for Duplicate Scans

For DXA scans of spine and femur where duplicate measurements are taken, the mean of duplicate records will be used for analysis.

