10.6 Efficacy Analyses

All statistical testing will be 2-sided. The baseline value of BMD and machine type will be included in the statistical model for primary and secondary efficacy analyses. For each of the efficacy BMD endpoints (lumbar spine, total hip, and femoral neck at Month 6), descriptive statistics will be provided for **actual** values and percent change from baseline at post-baseline visit by machine type and visit.

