10.6.3 Analyses of Exploratory Efficacy Endpoints

For P1NP and CTX, descriptive statistics will be presented by treatment group at each visit for both absolute values, change from baseline and the percent change from baseline values. Graphs depicting median and interquartile ranges by treatment group for percent change over time will be provided. The significance of the treatment difference for the percentage change from baseline at each visit will be assessed using a Wilcoxon Rank-Sum test. SAS code fragments are provided in Appendix 13.2.2.

The BTM efficacy analysis subset will be used for these analyses.

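### SAP 10.6.3 compares P1NP and CTX between arms only by an unadjusted Wilcoxon test; its visible text plans no baseline covariate and no between-arm estimate with a confidence interval

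*Protocol*

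**What the plan says.** - Protocol 1.3 sets a comparative objective: "To evaluate the effect of treatment with romosozumab for 6 months compared with placebo on percent changes in bone turnover markers (BTM").
- The protocol synopsis and Protocol 10.5.4 plan summaries and graphs by arm and name no test: "For P1NP and CTX, descriptive statistics will be presented by treatment group at each visit for both actual values and the percent change" from baseline. Protocol 10.4.2 treats any inference on these endpoints as exploratory.
- SAP 10.6.3 repeats the summaries ("descriptive statistics will be presented by treatment group at each visit for both absolute values, change from baseline and the percent change from baseline") and the plots ("Graphs depicting median and interquartile ranges by treatment group for percent change over time will be provided"). It then adds the only between-arm analysis: "The significance of the treatment difference for the percentage change from baseline at each visit will be assessed using a Wilcoxon Rank-Sum test".
- SAP 6.6 defines percent change as "The change from baseline value divided by baseline value and multiplied by 100".
- SAP 10.1 undertakes to estimate romosozumab's effects as well as to test hypotheses.
- For BMD, SAP 10.6 states: "The baseline value of BMD and machine type will be included in the statistical model for primary and secondary efficacy analyses". SAP 10.6.1 and 10.6.2 report an adjusted difference in least-squares means with a 95% CI.
- Baseline markers are available. The Schedule of Assessments draws them on Day 1, and SAP 7.3 admits to the BTM analysis set only women who have a baseline value.

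**The concern.** Two things are missing for the markers that every BMD endpoint has.

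The first is a between-arm estimate with an interval. The objective asks how much romosozumab changes P1NP and CTX relative to placebo. The only formal answer in the visible text is a p-value at each visit.

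The second is the baseline marker as a covariate. Dividing by baseline does not remove its influence. A woman whose baseline happens to be low tends to show a larger percent rise, through regression to the mean. A two-group rank test leaves that predictable variation in the error. With about 27 women per arm, this can cost precision when the treatment difference is modest.

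**Working it through.** **The plan's own figure.** The only power statement concerns lumbar spine BMD (Protocol 10.2, SAP 3.2): 30 per arm, 10% dropout, difference 6.6, SD 3.9, two-sided 5%. With 30 × 0.9 = 27 per arm, the standardised effect is 6.6 / (3.9 × √(2/27)) = 6.22. Power is 99.998% by the noncentral t, so the stated figure of more than 99% reproduces. It says nothing about the markers.

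**Inputs for the markers.** The documents give no marker SD, effect size or correlation. Assumed: log-normal markers, log-scale SD 0.4 at both visits, true ratio romosozumab/placebo 0.80 (log 0.80 = −0.223), and baseline-to-visit correlation ρ of 0.3 to 0.9 on the log scale. The 27 per arm comes from the plan.

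**Formulas.** Percent change is an increasing function of value/baseline, so the Wilcoxon test on percent change is the same test as on log(value/baseline).
- Correlation of log change with log baseline: −√((1−ρ)/2).
- Unadjusted SE of the log ratio: 0.4 × √(2(1−ρ)) × √(2/27).
- Adjusted SE: 0.4 × √(1−ρ²) × √(2/27) × √(1 + 1/50). The last factor is the small cost of estimating the covariate.
- Variance ratio before that cost: (1−ρ²) / (2(1−ρ)) = (1+ρ)/2.
- Approximate power: Φ(0.223/SE − 1.96).

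| ρ | Correlation with baseline | (1+ρ)/2 | SE unadjusted / adjusted | Formula power, unadjusted / adjusted | Simulated power, Wilcoxon / log-ANCOVA |
|---|---|---|---|---|---|
| 0.3 | −0.59 | 0.65 | 0.129 / 0.105 | 41% / 57% | 36% / 55% |
| 0.5 | −0.50 | 0.75 | 0.109 / 0.095 | 54% / 65% | 49% / 63% |
| 0.7 | −0.39 | 0.85 | 0.084 / 0.079 | 75% / 81% | 70% / 78% |
| 0.9 | −0.22 | 0.95 | 0.049 / 0.048 | over 99% / over 99% | 99% / 99% |

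The formula column is a normal approximation to a t-type comparison, so it runs slightly high. The simulated values follow the same pattern, and repeat runs differ by at most three percentage points. Type I error is about 5% for both methods.

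In sample-size terms, 1/0.65 = 1.54 and 1/0.85 = 1.18. At ρ from 0.3 to 0.7, adjustment is therefore worth about 54% down to 18% more subjects, before the covariate cost.

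**Sensitivity to effect size** (same SD and sample size, Wilcoxon vs log-ANCOVA):
- Ratio 0.70: 88% vs 96% at ρ 0.5; 98% vs 99% at ρ 0.7.
- Ratio 0.60: 97% or more for both at every ρ tried.
- Ratio 0.50: 100% for both.
- A 1.3-fold rise: 56% vs 72% at ρ 0.4; 95% vs 97% at ρ 0.8.

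**Chance imbalance.** One SD of the between-arm difference in mean log baseline is 0.4 × √(2/27) = 0.109. At ρ 0.5, an imbalance of that size moves the unadjusted contrast by (1 − 0.5) × 0.109 = 0.054, or about 5.5% in the ratio (e^0.054 = 1.055). This is a shift conditional on the imbalance, not a bias over repeated randomisation.

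**The case against.** A rank test for skewed markers is a defensible choice. It holds its type I error, and it is less sensitive than a log-scale model to CTX values set to the quantification limit under SAP 9.3.2. The endpoints are exploratory and no decision or sample size rests on them. All of this stands. It argues for keeping the Wilcoxon test, not against adding an estimate. In simulation the advantage of adjustment persisted with unequal variances between arms and with values floored at a quantification limit.

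A reader might infer more than the documents support:
- *That each woman's baseline is ignored.* It is the denominator of percent change; what is absent is baseline as a covariate.
- *That only p-values will be reported.* Means, medians, SDs and quartiles by arm and visit are planned, with median and interquartile plots. The size of the effect can be read informally; the formal contrast and its interval are missing.
- *That the comparison is biased.* Randomisation makes it unbiased, and the 0.054 above is ordinary sampling variation.
- *That power is lost at a particular visit.* Protocol 2.2 reports that treatment "resulted in a transient increase of the bone formation marker P1NP and a decrease in the bone resorption marker serum CTX", but gives no size or timing, and the word transient is attached to P1NP only. The documents do not show that any planned visit has a small difference.
- *That no shift estimate exists anywhere.* The Wilcoxon code in SAP Appendix 13.2.2 is blacked out and might request one. The point covers the visible text only.

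**Conclusion.** The point holds for the visible text: SAP 10.6.3 plans an unadjusted Wilcoxon test on percent change as the only between-arm analysis of P1NP and CTX, with no baseline covariate and no between-arm estimate with a confidence interval. The missing estimate depends on no assumption, and it sits poorly with a comparative objective and with SAP 10.1.

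The loss of precision does depend on assumptions. Under those used here it is 19 percentage points of power at ρ 0.3 (55 − 36), 14 at 0.5 (63 − 49), 8 at 0.7 (78 − 70) and none at 0.9. It is material only for a modest effect with weak to moderate correlation. Validity is not in question and no primary or secondary conclusion is affected. Severity is low.

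**What to change.** In SAP 10.6.3, add at months 1, 3 and 6 an ANCOVA of log(value/baseline) on treatment and log(baseline), allowing unequal variances by arm as Protocol 10.5.2 does for BMD. Report the back-transformed ratio, or percent difference, with its 95% CI.

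Keep the Wilcoxon test as supportive, optionally with a Hodges-Lehmann difference and 95% CI. If a rank method is preferred, a rank ANCOVA on baseline keeps most of the gain: simulated power 51%, 60% and 77% at ρ 0.3, 0.5 and 0.7 with ratio 0.80. Align Protocol 10.5.4 with the SAP.

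The cost is some wording and a few lines of code, with no new data. The downside is a log-normal assumption, and values imputed at the quantification limit are treated as exact. SAP 9.5 already requires model assumptions to be checked, and the retained rank test is the back-up.
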